### **9.3 Study Dose of Sulindac**

The dose of sulindac in tablet form to be studied is 150 mg twice daily or b.i.d. This is an available formulation from the pharmacy.

#### *9.3.1 Rationale for drug and dose selection*

Sulindac and its metabolites have been widely investigated as potential anti-cancer agents for multiple malignancies (J. Cuzick et al. 2009). Exposure to sulindac, particularly the primary sulfide metabolite, at doses higher (micromolar) than needed for COX2 inhibition (nanomolar) results in cell cycle arrest in the G1 phase and induction of apoptosis (Han et al. 1998). The anti-proliferative (cytostatic) and pro-apoptotic (cytotoxic) actions of sulindac sulfide have been attributed to p53-dependent and -independent induction of the cyclin-dependent kinase inhibitor p21waf1/cip1 (Yang et al. 2001). In mouse models of colorectal carcinogenesis, p21 inactivation completely eliminates the anti-polyp activity of sulindac in Apc1638 (+/-) mice (Kelloff et al. 2006), suggesting that this pathway is essential to the anti-neoplastic effect of sulindac.

[name] in collaboration with [name] recently completed a randomized, open-label phase I biomarker study of sulindac to assess the effects of sulindac and its metabolites on a stable derivative of COX2-derived prostaglandins (13, 14-dihydro-15-keto prostaglandin A2 [PGEM]) and the NSAID-inducible pro-apoptotic growth differentiation factor (GDF-15) in nipple aspirate fluid (NAF) ([name] et al.). Thirty women were randomized to sulindac 150 mg qd versus sulindac 150 mg bid for a short duration of 6 weeks. Sulindac was well tolerated in the study. Sulindac intervention was associated, in a dose-independent manner, with a non-statistically significant decrease in NAF PGEM ( $p=0.10$ ). GDF-15 showed a borderline significant trend towards higher NAF levels in the sulindac 150 mg bid intervention arm ( $p=0.07$ ). These data suggest that COX2 inhibition in the breast may be achieved at 150 mg sulindac qd, while a higher dose may be needed to fully realize COX-independent benefits, such as induction of anti-apoptotic factors (e.g., GDF-15). Because xenograft studies suggest the mechanism of decreased tumor growth is related to pro-apoptotic effects of sulindac on established tumors, and greater pain and joint stiffness relief is achievable with higher doses, we have selected the higher 150 mg bid as the intervention dose for the proposed study. Sulindac is readily and commercially available in 150 mg and 200 mg tablets for oral administration.

## **10 TOXICITY FOR SULINDAC- REPORTED ADVERSE EVENTS AND POTENTIAL RISKS**

### **10.1 Peptic ulcer and gastrointestinal bleeding**

These side effects have been reported in participants receiving Sulindac. Fatalities have occurred. Risk is higher among individuals over the age of 65. GI bleeding is associated with higher morbidity and mortality in participants with impaired by other medical conditions including hemorrhagic disorders. Combined use of NSAIDs with a proton pump inhibitor (PPI) such as omeprazole at 20 to 40 mg daily is associated with a 3-4 fold reduction in incidence of NSAID-induced gastric and duodenal ulcers, erosion, bleeding and perforation in randomized clinical trials of *Helicobacter pylori* negative patients at increased risk of ulcer (60 year and/or history of ulcer)(Lanza et al. 2009). Current guidelines recommend daily use of PPIs for gastropreservation from NSAID induced peptic ulcer and bleeding in individuals at increased risk for NSAID associated adverse GI events (e.g., 65 years or older and/or history of GI ulcer or bleeding)(Lanza et al. 2009).

### **10.2 Serious GI toxicity**

Serious GI toxicity such as bleeding, ulceration and perforation can occur at any time with or without warning symptoms in participants treated with chronic NSAID therapy. Serious GI toxicity has been observed in approximately 1% of participants treated for 3-6 months with daily NSAIDs. Although alcoholism, smoking, history of GI disease put the participant at increased risk serious GI toxicities

have occurred in individuals with no identifiable risk factors. Elderly or debilitated participants tolerate bleeding and perforation less well than other groups and are highest risk for adverse, life threatening event. High doses of NSAIDs carry a greater risk of GI toxicity than lower dose. Daily use of PPIs significantly reduces the risk of serious GI toxicity due to erosion or ulceration including perforation in patients taking NSAIDs or COX-2 inhibitors.(Lanza et al. 2009).

### **10.3 Hypersensitivity**

Hypersensitivity is rare with fever, rash and other symptoms including abnormalities in liver function tests. Liver function tests should be administered prior to initiation of agent. If unexplained fever occurs or other evidence of hypersensitivity, drug should be discontinued.

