### **10.4 Hepatic effects**

Hepatic effects including findings consistent with cholestatic hepatitis occur rarely in participants on Sulindac. As with other NSAIDs, borderline abnormalities in liver function can occur in up to 15% of participants. Sulindac use of more than 600 mg per day has been associated with increased incidence of mild liver test abnormalities. If a participant with symptoms of liver dysfunction, agent should be discontinued and follow up tests performed.

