## **10.7 Pancreatitis**

Pancreatitis has been reported in participants using Sulindac. If pancreatitis develops, Sulindac should be discontinued in these individuals.

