### **22.2 End of Treatment**

Study drug discontinuation is the time when study agent(s) administration is permanently discontinued for any reason.

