### **22.3 Withdrawal of Participant from Study**

Participants will be withdrawn from the study under the following circumstances:

- a. Study closure,
- b. Unacceptable adverse event(s), as judged by the study physician,
- c. Participant decision to withdraw from the study or, in the judgment of the investigator, further participation would not be in the best interest of the participant,
- d. The participant is noncompliant with study procedures

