## **24 TOXICITY MONITORING AND RESPONSE PLAN**

Note: Risk for toxicity with sulindac increases with longer use ( $\geq 6$  months) and higher doses. Dose reductions of 50% to 150 mg qd will be allowed, and 2 drug holidays totaling no more than 4 weeks will be permitted. Participants will be advised not to use over-the-counter NSAIDs without first consulting study staff.

- a. Participants will receive a study log on which to record time of sulindac doses. Participants will be instructed to use the study log daily to record concomitant medication use and adverse events. Participants will be instructed to return the log at their 3 month visits for adverse event review and concomitant medication review by nurse coordinator.

- b. During the initial 6 weeks of heaviest in-home blood pressure monitoring, site study personnel will place telephone calls every two weeks ( $\pm 3$  days) to document these data reducing to monthly after the first 6 weeks on agent.
- c. Participants will be educated to contact us at any time during the study to report any adverse event that fails to resolve in 3 days or results in a visit to the doctor or hospital.
- d. Participants with two or more BP readings above 140/90 will be seen by the research nurse and evaluated for antihypertensive therapy.
- e. Participants who develop grade 2 hypertension as determined by CTCAE version 4.0 will be monitored more closely and offered dietary and/pharmacologic intervention. Participants who develop grade 3 or higher hypertension will be removed from study, and treated as medically indicated to control their blood pressure.
- f. Participants experiencing a  $\geq$  Grade 2 toxicity (NCI, CTCAE version 4), regarded as possible, probable or definitely related to study agent during the study agent administration period will suspend the study agent(s) for a maximum of 2 consecutive days per event.
- g. With any NSAID trial, GI upset requiring dose reductions or the temporary need to take an NSAID may arise. Dose reductions of 50% to 150 mg qd will be allowed until symptoms resolve or indefinitely, and 2 drug holidays totaling no more than 4 weeks will be permitted during the study period.
- h. If the event remains unresolved at lower dosing, the participant will discontinue study agent and end of treatment procedures will be performed.
- i. If the event resolves, the participant will resume the original study schedule.

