- j. Study agent will be discontinued if the same event which caused suspension of the study agent occurs more than twice during the study.
- k. Participants that miss  $>28$  days of study agent during the study agent administration period, regardless of cause, will discontinue study agent and proceed with end of treatment procedures.
- l. Participants experiencing a  $\geq$  grade 2 toxicity possibly, probably, or definitely related to study agent will reduce dose by 50% if symptoms resolve within 7 days. If the symptoms recur on lower dose, the subject will be withdrawn from study and proceed with end of treatment procedures.
- m. Only one dose modification will occur in this study.

For the observational group, there is no toxicity or risk associated with this study. Thus participants will not be followed past conclusion of the study. No toxicity data will be collected and no adverse events are to be expected.

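### For related grade 2 or higher hypersensitivity, liver-dysfunction symptoms or pancreatitis, Section 10 stops sulindac but Section 24 items f and l allow a short hold or half dose, with no exception

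*Protocol*

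**What the plan says.** Three subsections of protocol Section 10 give a stopping instruction, none with a grade threshold:

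- 10.3, hypersensitivity: "If unexplained fever occurs or other evidence of hypersensitivity, drug should be discontinued".
- 10.4, hepatic effects: "If a participant with symptoms of liver dysfunction, agent should be discontinued and follow up tests performed".
- 10.7, pancreatitis: "If pancreatitis develops, Sulindac should be discontinued in these individuals".

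Section 22.2 describes discontinuation: "Study drug discontinuation is the time when study agent(s) administration is permanently discontinued for any reason".

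Section 24 has two general rules for toxicity of grade 2 or higher judged possibly, probably or definitely related to the study agent. Under item f the participant "will suspend the study agent(s) for a maximum of 2 consecutive days per event". Under item l she "will reduce dose by 50% if symptoms resolve within 7 days", and is withdrawn if symptoms recur on the lower dose. Section 24 mentions none of the three events and does not refer back to Section 10.

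Section 22.3 lists grounds for withdrawal, among them "Unacceptable adverse event(s), as judged by the study physician" (item b) and the investigator's judgment that "further participation would not be in the best interest of the participant" (item c).

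**The concern.** For one class of events the protocol gives a site two different instructions. A woman with, say, a related grade 2 hypersensitivity reaction that settles in a few days should come off sulindac under Section 10.3. Under Section 24 item l she stays on it at half dose. Section 24 is where staff would look for what to do, and it does not tell them that these events are different. Section 19 makes the two centers separately responsible for toxicity monitoring, so they could resolve the conflict differently.

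What is at stake is further exposure to sulindac after an event for which the protocol itself says to stop. No efficacy estimate is involved.

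**Working it through.** No sample size, power or error-rate figure enters, so the check compares the texts.

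**1. Same event, two instructions.** The full dose is 150 mg × 2 = 300 mg a day. Halved, it is 300 × 0.5 = 150 mg a day, which matches the reduced dose given in Section 24.

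| Event (grade 2 or higher, at least possibly related) | Section 10 | Section 24, items f and l |
|---|---|---|
| Hypersensitivity, including unexplained fever | Stop (10.3) | Hold at most 2 consecutive days; 150 mg a day if symptoms resolve within 7 days |
| Symptoms of liver dysfunction | Stop and test (10.4) | Same |
| Pancreatitis | Stop (10.7) | Same |

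**2. Does 'discontinued' mean more than 'held'?** Sections 10.3, 10.4 and 10.7 do not say that the stop is permanent. Two things support that reading. Section 22.2 treats study drug discontinuation as permanent. Section 24 keeps the terms apart: item f suspends, while items h and k pair discontinuation with end-of-treatment procedures.

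**3. Is Section 10 meant to be acted on?** Its title presents it as a list of reported events and risks, but the three sentences are directive. The blood-pressure actions in 10.6 also reappear in Section 24: evaluation after two or more readings above 140/90 becomes item d, and the grade 2 and grade 3 hypertension rules become item e. One subsection's rules were carried over and three were not.

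**4. Does anything in Section 24 stop the drug at the first such event?** The other routes to stopping are:

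- item h: the event is unresolved at the lower dose;
- item j: the same event causes suspension more than twice;
- item k: more than 28 days of agent are missed;
- item l: symptoms recur at the lower dose.

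None requires a stop at the first occurrence of an event that resolves. Only item e does so for a named event, grade 3 or higher hypertension.

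**5. Scope.** Items f and l do not reach grade 1 or unrelated events. Continued dosing under item l further requires resolution within 7 days. The conflict is therefore confined to related grade 2 or higher events of these three types, and is sharpest for those that resolve within 7 days.

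**The case against.** The strongest case is that the sections can be read together. Section 10 is specific and Section 24 general, and a drug already stopped under 10.3, 10.4 or 10.7 cannot then be held or halved. Section 22.3 adds a safeguard with a mandatory lead-in: a participant with an adverse event that the physician judges unacceptable will be withdrawn. Permanence is also an inference. Section 22.2 defines a time point under an end-of-treatment heading, and the legend to Figure 1 uses 'discontinue' for the temporary NSAID washout and observation period.

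Part of this stands. A careful reader may well apply the specific rule, and the physician can always stop the drug. But the protocol states no precedence, and 22.3 depends on a judgment and names none of the three events. The washout wording concerns participants' own NSAIDs, not the study agent. These points soften the conflict without removing it.

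Three stronger readings are tempting and are not supported:

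- *Return to full dose.* Item i resumes the original schedule once an event resolves, but it follows the gastrointestinal items g and h and may apply only to them. The point rests on item l and half dose.
- *A measurable amount of extra exposure.* The documents give no onset times and no restart date. Hypersensitivity and cholestatic hepatitis are called rare, and pancreatitis has no stated rate. Any count of extra treatment days would rest on invented inputs.
- *An effect on the results.* The SAP's tolerability hypothesis concerns grade 3 events and dropout due to adverse events. The SAP does not say that stopping sulindac counts as dropout, and the documents report no affected woman.

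**Conclusion.** The inconsistency is real and minor. For related grade 2 or higher hypersensitivity, symptoms of liver dysfunction or pancreatitis, Section 24 read literally permits a hold of at most 2 days and then half dose where Section 10 says to stop. The conclusion assumes that 'discontinued' in Section 10 means a permanent stop, as Section 22.2 and the usage in Section 24 suggest, and that sites could apply Section 24 as written.

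No endpoint, power figure or event rate is affected. Section 4.4 records that accrual and participation have concluded, so rewording protects no current participant. A reader might infer that women were wrongly kept on sulindac; the documents do not show that any were.

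**What to change.** Add one sentence to Section 24: *Evidence of hypersensitivity (including unexplained fever), symptoms of liver dysfunction, or pancreatitis leads to permanent discontinuation of sulindac at first occurrence, with no rechallenge or dose reduction; this overrides items f, i, j and l; endpoint follow-up continues if the participant agrees.* Naming item i settles its uncertain reach for these events. The follow-up clause matches what Section 10.6 already provides after a hypertension stop.

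The cost is that one sentence, with no new data and no change to sample size or analysis. With participation over, its practical use is where the text is reused, for example in the larger trial that Section 5.8 foresees. The SAP needs no change: it already commits to reporting all adverse events in the sulindac group, and Section 30.1 records the action taken for each.

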### **10.4 Hepatic effects**

Hepatic effects including findings consistent with cholestatic hepatitis occur rarely in participants on Sulindac. As with other NSAIDs, borderline abnormalities in liver function can occur in up to 15% of participants. Sulindac use of more than 600 mg per day has been associated with increased incidence of mild liver test abnormalities. If a participant with symptoms of liver dysfunction, agent should be discontinued and follow up tests performed.

### **10.5 Platelet effects**

Though less active than aspirin at inhibiting platelet function, Sulindac is an inhibitor of platelet function and affects coagulation function.

### **10.6 Cardiovascular**

Recent findings regarding selective COX-2 inhibitors have raised the possibility that non-selective NSAIDs, including sulindac, may increase cardiovascular risk, presumably to the extent that they inhibit COX-2. While not completely elucidated, the predominant theory regarding the increased cardiovascular events associated with NSAID use is thought to be secondary to the reduction in biosynthesis of PGI2 and PGE2 in the kidney and vessel wall. PGI2 is a potent vasodilator that also reduces platelet aggregation in response to agonists. Thus, the preferential effects of COX2 inhibition in decreasing PGI2 does not offset the lesser effects of COX1 inhibition on thromboxane (TxA2) synthesis resulting in net vasoconstriction and increased platelet reactivity. Patients with pre-existing vascular disease and poor vasodilatory responses, i.e. decreased vascular nitric oxide biosynthesis in diabetes and active smokers, would be predisposed to cardiovascular events (Marnett 2009). Patients with risk factors including advanced age, smoking, diabetes, hypertension, hyperlipidemia, and prior

history of cardiovascular disease were at markedly higher risk of cardiovascular events in clinical trials of coxibs suggesting the risk/benefit ratio could be markedly improved by selecting low risk patients as we have done for our proposed trial (Solomon et al. 2008). There are only scant data regarding the association of sulindac, in particular, with risk of cardiovascular endpoints: in one large study there was no association between use of the drug and myocardial infarction. Because of their effects on renal prostaglandins, most NSAIDs have the potential to increase blood pressure and interfere with blood pressure control in hypertensive participants. Sulindac sulfite, the active metabolite of sulindac, is tightly protein-bound and so not filtered by the kidneys, and therefore apparently has less effect on blood pressure control than other NSAIDs (Spence 2007, 1986; Abate et al. 1990; Beermann et al. 1986; Koopmans et al. 1984; Koopmans et al. 1986; Lauven et al. 1990; Wong et al. 1986). We have now added a fourth aim to study the effects of sulindac on blood pressure as a plausible inexpensive and readily available biomarker of NSAID risk. Patients will be given a validated, semiautomatic electronic home blood pressure monitoring device to serially measure their blood pressure in triplicate each morning and evening for 3 days every 2 weeks for the first 6 weeks on agent and in last month of therapy. Patients with two or more BP readings above 140/90 will be seen by the research nurse and evaluated for antihypertensive therapy. Patients who develop grade 2 hypertension as determined by CTCAE version 4.0 will be monitored more closely and offered dietary and/pharmacologic intervention. Patients who develop grade 3 or higher hypertension will be removed from study intervention treated as medically indicated to control their blood pressure, and continue being followed to the end of the study as described in this protocol if participant agrees.

## **10.7 Pancreatitis**

Pancreatitis has been reported in participants using Sulindac. If pancreatitis develops, Sulindac should be discontinued in these individuals.

## **10.8 Other**

There have been reports of acute interstitial nephritis with hematuria, proteinuria and occasionally nephritic syndrome.

## **11 INFORMATION ON BREAST IMAGING PROCEDURES AND RISKS**

All participants will undergo breast imaging by non-contrast MRI to obtain three-dimensional (3D) FWR and ADC mapping. Participants on the observational AI alone are will receive an MRI at baseline, 6 and 12 months. The participants on the sulindac arm will receive an MRI at baseline 1 and 2, and 6 months, and 12 months. All imaging procedures will adhere to FDA and OSHA guidelines. Images will

be acquired using an 8-channel phased array, dual breast coil on a Siemens 3.0 T MRI 16-Channel AI Breast Coil scanner on site at Arizona's University Medical Center and Stony Brook Hospital. The MRI facility is shared by the hospital and research investigators with dedicated time to research and support staff for research studies.

### **11.1 FWR-MRI methods**

Fat-water imaging will be performed using the radial Gradient-Echo and Spin-Echo (GRASE) technique developed by co-investigator [name] (Li et al. 2009). This method provides a robust lipid/water separation, which includes correction for field inhomogeneity and T2 decay. Radial scanning provides robustness to motion. Data are acquired with various phase shifts between the fat and water signals. The separation of fat and water is then performed using an iterative algorithm (Reeder et al. 2004). The specific sequence parameters to be used are the following: TR=6000 ms, ETL=8, matrix size=256x256, number of averages=1, slice thickness=7 mm, and FOV=34x34 cm^2. Axial slices will be prescribed such that both breasts are imaged completely. For fat-water separation, four gradient echoes per spin echo period will be collected with phase shifts: (-5π/6, -π/6, π/2, 7π/6) and receiver bandwidth of ±125 kHz, yielding ~18-19 slices in ~3 min.

### **11.2 Diffusion-weighted MRI**

As a secondary objective, we are exploring the potential of diffusion weighted MRI (DW-MRI) of the breast as a quantitative and qualitative imaging approach to obtain information that reflects differences at a cellular level by providing unique insights about tissue cellularity and the integrity of cellular membranes ('functional imaging'). DW-MRI has been actively pursued by our group and others for the early assessment of tumor response to treatment (Pereira et al. 2009; Theilmann et al. 2004; Woodhams et al. 2005; Abdel Razek et al. 2010; Peters et al. 2010). In the proposed study, DW-MRI will be performed to determine the ADC of water in the parenchymal/stromal tissue of the normal breast. This is a highly novel application of this technology. To minimize the effects of participant motion, a single shot echo planar imaging (SSEPI) imaging sequence will be employed. Images will be obtained at the same axial locations and FOV as in the FWR-MRI, with a TR = 6000 ms, TE=75 ms and matrix size = 128x128. ADC maps will be calculated from the exponential decay of signal between two SSEPI images, with and without diffusion weighting (b=0 and 400 s/mm^2).

